Contrasting Dosivent with Plus Flow Vu Spacer in Bronchial Hiperreactivity Patients

NCT: N/A

Date: 01/march/2022

Contrasting Dosivent with Plus Flow Vu Spacer in Bronchial Hyperreactivity Patients

Inhaled medication is the first-line treatment for diseases such as asthma or chronic obstructive pulmonary disease. Its effectiveness is related to the amount of drug that manages to be deposited beyond the oropharyngeal region, with the place where the deposit occurs and with its uniform distribution or not. Other important factors are the size of the inhaled particles, breathing conditions, airway geometry, and mucociliary clearance mechanisms.

The respiratory system is specially designed both anatomically and functionally, so that the air reaches the most distal territories in the best clean conditions. The hairs of the nose, the heat turbines of the nostrils, the vocal cords, the cilia of the bronchial epithelium, the sneezing and coughing reflexes, etc., contribute to carrying out this work in the most appropriate way.

The size and shape of the particles are essential factors that will determine their deposit in the lung. The size is defined by what is called the diameter of the mean aerodynamic mass (DMMA) or diameter of a particle of mass equal to the median of the particles of a population, that is to say, that diameter of the particle in which 50% of the mass of the aerosol is above it and the other 50% below. Depending on their size and shape, particles can be deposited by four mechanisms:

Shock. It is the physical phenomenon by which aerosol particles tend to continue with their trajectory when they pass through the airways, instead of adapting to the curvatures of the respiratory tract. Particles with sufficient momentum (mass times velocity) will be affected by centrifugal forces at those points where the airflow changes direction suddenly, hitting the airway wall. This happens mainly in the first 10 bronchial generations, in which the air velocity is high and the flow is turbulent. This phenomenon mainly affects particles larger than 10 μ m, which will be retained mainly in the oropharyngeal region, especially if the drug is administered using powder inhalers (PSI) or pressurized cartridge inhalers (PCI).

Intercept. It occurs mainly in the case of fibers, in which, due to their elongated shape, the deposition occurs as soon as they come into contact with the airway wall.

Sedimentation. It is the physical phenomenon by which particles with a sufficient mass are deposited by gravity when the time spent in the airway is long enough. It predominates in the last 5 bronchial generations, in which the air velocity is low and, therefore, the residence time is prolonged.

Suspension. It is the phenomenon by which the particles of an aerosol move erratically from one place to another in the airways. It happens as a consequence of the Brownian movement of the particles and occurs in those with a size of less than 0.5 μ m of DMMA when they reach the alveolar spaces, where the air speed is practically zero. These particles usually do not settle and are expelled back to the outside with the expiration.

Aerosolized drug particles usually have a uniform shape, with symmetry in several planes and are rarely less than $1\mu m$ in size, so the predominant mechanisms will be shock and sedimentation.

In general, it can be considered that particles with DMMA greater than 10 μ m are deposited in the oropharynx, those of 5-10 μ m in the central airways, and those of 0.5-5 μ m in the small airways and alveoli. Therefore, for topical respiratory treatment, it is interesting to use

particles with DMMA between 0.5 and 5 μ m. It is what is called the respirable fraction of an aerosol.

One way to avoid miscoordination between the patient and the device is inhalation chambers, which attach to the mouthpiece of the ICP. The aerosol passes into the chamber and the overly large particles hit its walls, being retained in it, while the smaller particles remain in suspension inside the chamber until they are inhaled by the patient. In addition, the space provided by the chamber between the ICP and the patient's mouth allows the aerosol to slow down, reducing the impact against the oropharynx. In this way, local adverse effects are reduced and the pulmonary deposition of the drug is increased. ICPs used with an inhalation chamber have been shown to be as effective as nebulizers in the treatment of acute asthma attacks.

Also, with the aim of avoiding activation-inhalation incoordination, ICPs have been developed that are triggered automatically with the patient's inspiration, such as the Autohaler® and Easybreath®, which have been shown to improve the pulmonary deposition of the drug in patients with coordination difficulties. They also require a lower inspiratory flow than conventional ICPs, around 18-30 L/min, which makes them more suitable for patients with physical limitations, children, and the elderly.

Primary Objectives

- Compare the efficacy, as measured by changes in forced expiratory volume in the first second (FEV1) in miliLiters of inhaled Salbutamol with the Dosivent® chamber versus the widely used Aerochamber Plus® Flow-Vu® in patients with a positive Bronchodilator testing.
- Compare the efficacy, as measured by changes in forced expiratory volume in the first second (FEV1) in percentage of inhaled salbutamol with the Dosivent® chamber versus the widely used Aerochamber Plus® Flow-Vu® in patients with a positive Bronchodilator testing.

Secondary Objectives

- Compare the efficacy, as measured by changes in forced vital capacity (FVC) in miliLiters, of inhaled Salbutamol with the Dosivent® chamber versus the widely used Aerochamber Plus® Flow-Vu® in patients with a positive Bronchodilator testing.
- Compare the efficacy, as measured by changes in forced vital capacity (FVC) in percentage, of inhaled Salbutamol with the Dosivent® chamber versus the widely used Aerochamber Plus® Flow-Vu® in patients with a positive Bronchodilator testing.

Number of Patients

Approximately 50 patients with a diagnosis of Bronchial Hyperreactivity will be included in the study.

Methodology

The investigators are conducting a non-randomized, open-label, crossover-controlled clinical trial in 50 patients with a previous positive bronchodilation testing. The protocol was approved

by the local clinical ethics committee (code 03/2022). All participants provided written informed consent before any study procedure. During the study, the principles of the Declaration of Helsinki and the current standards of Good Clinical Practice were followed.

Participants over 18 years of age are included who attended our center for a bronchodilator test, gave a positive result in this test, and provided written informed consent for participation in this study. Patients are excluded if grade A quality spirometry was not obtained according to the classification in current regulations and, in the opinion of the investigator, performing a bronchodilator test could pose a risk to the patient or interrupting the usual bronchodilator treatment could worsen the underlying respiratory pathology.

Inclusion Criteria:

- Patients over 18 years of age
- Attending our center for a bronchodilator test
- Positive bronchodilator result with increase of Forced Expiratory Volume in first second greater than 200mL and 12%
- Provided written informed consent for participation in this study

Exclusion Criteria:

- Grade A quality spirometry was not obtained according to the classification in current regulation
- Performing a bronchodilator test, in the opinion of the investigator, could pose a risk
 to the patient or interrupting the usual bronchodilator treatment could worsen the
 underlying respiratory pathology.

Determination of sample size

To achieve a statistical power of 80% in order to detect differences in the test of the null hypothesis H_0 : μ_1 - μ_2 = 0 for two related samples, with a significance level of 0.05, it will be necessary to include 45 patients in the study. Taking into account that the expected percentage of dropouts is 5%, it would be necessary to recruit 50 subjects for the study.

Statistical Methods

The primary analysis will be performed by intention to treat according to the following table:

Population	Description All patients registered in the study database; includes both screened participants and participants who are not selected but sign the informed consent (IC) form	
All patients included		
By modified intention to treat	All randomized patients receiving at least one dose of study treatment. Participants will be analyzed according to the treatment to which they were randomly assigned. The intention-to-	

	treat population will be used for all efficacy summaries	
Protocol population (PP)	The PP is comprised of the intention-to- treat population, excluding any participant with a major deviation from the protocol. The PP will be used to present sensitivity analyzes for the key endpoints.	
Safety population	All randomized participants receiving at least one dose of study treatment. Participants will be analyzed according to the treatment they actually received. The safety population will be used for all safety summaries	

Parameter differences will be described as mean and standard deviation if the normality of the mean differences can be verified; otherwise, they will be described as median and interquartile range. The proportions will be described with their standard error.

Study variables will be analyzed using linear mixed models representing repeated measures in which patient will be the random effect and treatment and study phase will be the fixed effects.

Schedule of Activities (SoA)

Visit 1		Visit 2	
Informed Consent	X		
Inclusion and Exclusion	X		
Criteria			
Medical History	X		
Inhaled Therapy Medication	X		
Randomization	X		
Spirometry with	X	X	
Bronchodilator Testing			
Clinical Registry	X	X	

Procedures

Informed consent must be signed prior to any screening assessment.

Patients with Bronchial Hyperreactivity, defined by a positive Bronchodilator Test, will be offered the study through a patient information sheet and informed consent from the patient. A positive bronchodilator test is defined as patients with an improvement in forced expiratory volume in the first second (FEV1) of 200mL and an increase of 12% after 15-30 minutes of application of 4 puffs of Salbutamol in a pressurized cartridge with the Aerochamber Plus Flow air chamber. Vu according to usual clinical practice. Once the patient has signed the informed consent, they will be summoned to perform said test again on another day, having already passed the 6-hour Salbutamol washout period. Subsequently, a comparison will be made with a Delta limit of non-inferiority of 3%.

Bibliography

- Byron P. Drug Delivery Devices. Issues in Drug Development. Proc Am Thorac Soc Vol 1.
 Pp. 321-328, 2004.

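### The trial is called non-randomized, but its analysis populations and schedule require randomisation; the chamber used at each visit is unstated, so the device effect may be inestimable or mixed with a visit effect

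*Combined protocol and SAP*

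**What the plan says.** On assignment, the plan makes two kinds of statement.

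- Methodology calls the study a "non-randomized, open-label, crossover-controlled clinical trial in 50 patients with a previous positive bronchodilation testing".
- Statistical Methods defines the modified intention-to-treat population as "All randomized patients receiving at least one dose of study treatment" and adds that "Participants will be analyzed according to the treatment to which they were randomly assigned". Of the intention-to-treat set it says that the "treat population will be used for all efficacy summaries". The per-protocol population is a subset of it.
- The safety population is "All randomized participants receiving at least one dose of study treatment".
- The Schedule of Activities has a Randomization row, marked at Visit 1, and shows spirometry with bronchodilator testing at both visits.

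The model is a linear mixed model in which "patient will be the random effect and treatment and study phase will be the fixed effects". *Study phase* is not defined.

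On chamber order, Procedures names only the Aerochamber, as the chamber used in usual practice for the test that qualifies the patient. After consent the patient is recalled on another day, once the 6-hour salbutamol washout has passed, to repeat the test. The chamber for the repeat is not named. Dosivent appears in the title and objectives but is never attached to a visit. Entry requires "Positive bronchodilator result with increase of Forced Expiratory Volume in first second greater than 200mL and 12" per cent. Methodology states that "All participants provided written informed consent before any study procedure", and Procedures requires consent before any screening assessment.

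**The concern.** A trial cannot be non-randomized and also analyse only its randomized patients by their random assignment. The contradiction reaches every efficacy and safety summary, because it sits in the definitions of the sets on which they are run.

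The missing chamber order matters because a crossover separates device from occasion only if both orders occur. If all patients follow one order, the device contrast and the difference between visits are the same contrast. The quantity to be judged against the 3% non-inferiority margin would then be either inestimable or a mixture of device and visit.

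The status of the qualifying test raises a further issue. If that Aerochamber test also serves as the reference period, one of the two results being compared was selected for being high and the other was not.

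**Working it through.** **1. The plan's own figures.** The sample size (45 evaluable, 50 recruited) is given without an effect size or SD, so 45 can be neither reproduced nor refuted. This point does not dispute it; 45 and 50 are used below only as numbers of patients.

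**2. The statements on assignment, side by side.**

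| Place | Randomised? | If the trial is not randomised |
|---|---|---|
| Methodology | No | – |
| Modified intention-to-treat | Yes | No patient qualifies |
| Per-protocol | Yes, as a subset | No patient qualifies |
| Safety | Yes | No patient qualifies |
| Schedule of Activities | Yes | The row has no content |

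One design label stands against two population definitions, the set that inherits from the first of them, and a schedule row.

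**3. Is the qualifying test a study period?** The text points both ways. Testing described as previous, consent before any study procedure, and randomisation at Visit 1 suggest a separate qualifying test followed by two study tests. The single recall in Procedures suggests that the qualifying test is the Aerochamber period and the recall is the Dosivent period. Nothing settles it.

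**4. Estimability if phase means visit.** Code each row as (intercept, treatment, phase), with Aerochamber = 0, Dosivent = 1, first visit = 0 and second visit = 1.

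- All Aerochamber first: rows (1,0,0) and (1,1,1). Treatment equals phase; rank 2 of 3.
- All Dosivent first: rows (1,1,0) and (1,0,1). Treatment equals intercept minus phase; rank 2 of 3.
- Both orders used: all four rows occur; rank 3 of 3.

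A random patient effect does not alter the rank of the fixed effects. Under a single order the device effect is therefore not estimable.

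**5. A single order with phase dropped, or with phase meaning before and after bronchodilator.** The columns are no longer aliased and the model can be fitted. Let τ be the device effect and π the second-minus-first visit effect. The Dosivent-minus-Aerochamber difference estimates τ + π if Aerochamber is first and τ − π if Dosivent is first. The visit effect enters one for one.

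**6. Precision if both orders are used.** With n1 and n2 patients in the two orders and n = n1 + n2, regress each patient's visit difference on an intercept and an order indicator of ±1. Then Var(τ) = SD_d² / (4·n1·n2/n). Relative to the plain paired comparison, SD_d²/n, the ratio is n² / (4·n1·n2).

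| Split | Variance ratio | SE ratio |
|---|---|---|
| 25/25 | 2500/2500 = 1.0000 | 1.000 |
| 23/22 | 2025/2024 = 1.0005 | 1.0002 |
| 25/20 | 2025/2000 = 1.0125 | 1.006 |

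The 25/20 row is a deliberately unfavourable case: five losses of 50 (10%, against the planned 5%), all in one order. Estimating phase takes one degree of freedom: the two-sided 5% t critical value at n = 50 moves from 2.010 (49 df) to 2.011 (48 df).

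**7. Selection, if the qualifying test is the reference period.** Admitting only patients whose Aerochamber result exceeded 200 mL and 12% makes the expected measurement error of that result positive. The later Dosivent result is not selected. The difference is therefore shifted against Dosivent. Its size needs the mean response and the between- and within-patient SDs, and the documents give none of these.

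**The case against.** The strongest reply is that the contradiction is real but the statistical damage is not shown. *Study phase* is undefined; in a repeated-measures analysis of spirometry before and after salbutamol it could mean exactly that, and the model could then be fitted under any chamber order. This stands. A reader might infer that the planned model cannot estimate the device effect, but the documents support that only if the order is the same for everyone and phase means visit. What survives under the other meaning is confounding of device with visit if the order is fixed.

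A reader might also take the order to be Aerochamber then Dosivent and attach a figure to regression to the mean. The text does not establish that order, and any figure would rest on invented means and SDs.

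It may further be said that randomising the order is not free. This also stands in part. A separate qualifying test plus one test per chamber makes three tests, whereas Procedures describes a qualifying test and one recall. If Visit 1 is itself the qualifying test, randomising the order needs one more.

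Finally, a fixed order may be deliberate, since the only explicit design label is *non-randomized*. That is a legitimate choice, but the population definitions and the schedule would then be wrong. None of these replies removes the contradiction or supplies the chamber at each visit.

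**Conclusion.** With high confidence, the plan contradicts itself on randomisation, and it does not say which chamber is used at which visit. The analysis sets and the assignment rule cannot be applied as written, so this must be fixed.

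With medium confidence, and only if the order is the same for all patients and phase means visit, treatment and phase are fully aliased (rank 2 of 3). If the order is fixed but phase is dropped or means before and after bronchodilator, the estimate exists but carries the whole visit effect, in either direction. If, in addition, the qualifying Aerochamber test is the reference period, regression to the mean works against Dosivent in the comparison with the 3% margin. Neither bias can be sized from the documents. If both orders are used after a separate qualifying test, neither the aliasing nor the differential selection arises.

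**What to change.** Reconcile Methodology, Statistical Methods, the Schedule of Activities and Procedures. Define *study phase*, name the chamber at each visit, and state whether the qualifying test is an analysed period. Then take one of two routes.

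**(a) Both scheduled spirometries follow a separate qualifying test.** Delete *non-randomized*; randomise order 1:1 (Aerochamber–Dosivent or Dosivent–Aerochamber), as the populations and schedule already require; keep treatment and visit in the model. The cost is an order list and wording, with an SE ratio of 1.000 at 25/25. If Visit 1 is itself the qualifying test, this route needs one more test and is not free.

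**(b) A fixed order is intended, whether or not the qualifying test is the Aerochamber period.**

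- Remove the Randomization row and the references to randomized patients and random assignment.
- Define the efficacy set as enrolled patients tested with Dosivent after consent, and the safety set as enrolled patients receiving at least one study dose after consent. Without the reference to consent, a qualifying dose counted as study treatment would admit everyone.
- Do not fit a visit term alongside treatment.
- Limit the conclusion to a single-sequence comparison that cannot separate device from visit effects.
- If the qualifying test is the reference period, also state that the comparison is subject to regression to the mean, and reconcile the consent statements in Methodology and Procedures with a reference test done before consent.

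The price of (b) is a weaker conclusion.

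### The sample size rests on a paired test of equality, but the comparison is to use a 3% non-inferiority limit; nothing connects the two, so the 80% power is not shown to apply to non-inferiority

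*Combined protocol and SAP*

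**What the plan says.** Three places in the combined protocol and SAP bear on this point.

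- **Determination of sample size.** The calculation is framed as "To achieve a statistical power of 80% in order to detect differences in the test of the null hypothesis" that the two means are equal (H0: μ1 − μ2 = 0), "for two related samples, with a significance level of 0.05, it will be necessary to include 45 patients in the study". Recruitment is then set at 50 to allow for dropout. The section gives no detectable difference, SD of paired differences, sidedness or margin.
- **Procedures.** After describing the repeat bronchodilator test, the section ends: "Subsequently, a comparison will be made with a Delta limit of non-inferiority of 3" per cent. The margin appears nowhere else.
- **Primary Objectives.** There are two. One reads "Compare the efficacy, as measured by changes in forced expiratory volume in the first second (FEV1) in miliLiters of inhaled Salbutamol" with each chamber; the other is the same comparison in percentage terms ("Compare the efficacy, as measured by changes in forced expiratory volume in the first second (FEV1) in percentage of inhaled salbutamol"). Neither mentions non-inferiority.

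Statistical Methods specifies a linear mixed model in which "patient will be the random effect and treatment and study phase will be the fixed effects". It gives no confidence level, one-sided test or rule for comparing the treatment contrast with a limit.

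**The concern.** A test of equality and a test of non-inferiority answer different questions. Rejecting equality shows that the devices differ, but not whether the difference lies within a tolerated limit. Failing to reject equality shows neither that they are the same nor that one is not worse. The plan therefore has a margin with no rule for using it, and a null hypothesis that cannot deliver the conclusion the margin implies.

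The primary conclusion is at stake. The same data could be reported as no significant difference, as a significant deficit or as non-inferior, and the plan does not say which reading governs. The 3% could be percentage points of FEV1 change, a relative percentage or something else, and the mL objective has no limit at all. The quoted 80% power belongs to the equality test, and a reader cannot tell what power the non-inferiority comparison has.

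**Working it through.** **Inputs from the documents:** 45 evaluable pairs, 80% power, significance level 0.05 without sidedness (Determination of sample size); limit 3% without endpoint or scale (Procedures).

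**Assumptions, because the documents are silent:** 3% means 3 percentage points of FEV1 % change; SD of paired differences from 4 to 10 points; true difference 0 unless stated; one-sided 0.025 for non-inferiority, matching a two-sided 95% CI. The calculations use the noncentral t distribution with 44 degrees of freedom.

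**1. The plan's own figure.** With neither a detectable difference nor an SD, 45 can be neither reproduced nor refuted. Solving backwards, 45 pairs give 80% power for a standardised paired difference (difference/SD) of 0.427 at two-sided 0.05, or 0.376 at one-sided 0.05.

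**2. Do the two tests need different numbers?** For margin M and true difference 0, non-inferiority power is P(T > t), where T is noncentral t with noncentrality (M/SD)·√45 and t = 2.015. An equality test sized to detect a difference of M at two-sided 0.05 uses the same critical value and noncentrality (its opposite tail is negligible), so the required n is the same. For M = 3, 80% power at n = 45 needs SD ≤ 3/0.427 = 7.0. The figure of 45 could serve both tests, but only under conditions that the plan does not state.

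**3. Range over the unknown SD**, n = 45, margin 3. The middle column takes a true difference of 0. The last column is the probability that two-sided equality at 0.05 is not rejected when the new device is truly 3 points worse.

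| SD of paired differences | Power for non-inferiority | Equality not rejected at a true 3-point deficit |
|---|---|---|
| 4 | 99.8% | 0.2% |
| 5 | 97.6% | 2.4% |
| 6 | 90.7% | 9.3% |
| 7 | 80.3% | 19.7% |
| 8 | 69.2% | 30.8% |
| 10 | 50.3% | 49.7% |

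The last column matters only if a non-significant equality test were read as showing that the device is not worse. Under a 95% CI margin rule the corresponding error is 2.5% whatever the SD. The equality reading is no worse than that at SD 4 or 5, and much worse at SD 8 or 10.

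**4. The two rules can disagree in either direction.** The 95% CI half-width is 2.015 × SD/√45.

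- SD 10: half-width 3.0. An observed −1 gives −4.0 to 2.0. Equality is not rejected, yet a 3-point deficit is not excluded.
- SD 4: half-width 1.2. An observed −1.5 gives −2.7 to −0.3. Equality is rejected, yet the 3-point margin is met.

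**The case against.** The strongest reply is that 45 may be right for both purposes. If the sponsor sized the equality test for 3 points at two-sided 0.05 with an SD near 7, the same 45 gives about 80% power for non-inferiority with margin 3 and no true difference. This stands as far as it goes. A reader might infer from the mismatch that the trial is underpowered, and the documents do not support that: with an SD of 4 to 6, power would exceed 90%. But the favourable case also rests on values that are not in the plan.

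A second reply is that non-inferiority is plainly intended, so the null is only loosely worded. The word in the objectives is simply to compare, which fits either aim. Even if the reply is right, the null, the decision rule and the scale would still need to be written.

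A third reply is that nothing in the plan says a non-significant result will be taken as showing the device is not worse. That is correct. The last column of the table shows what that reading would cost, not what the plan commits to.

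**Conclusion.** The inconsistency is real and must be fixed. The only stated null is equality, the only stated limit is for non-inferiority, and no text joins them. The finding needs no assumption about the SD. What it establishes is a missing hypothesis and decision rule on the primary objectives, an undefined scale for the 3%, and no margin for the mL endpoint.

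It does not establish a power shortfall or an error in the number 45. The power figures are illustrations, conditional on the percentage-point reading, a true difference of 0 and an assumed SD; over SD 4 to 10 they run from 99.8% to 50.3%.

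Two neighbouring issues also affect whether the device contrast can be estimated and should be handled separately. First, Methodology calls the trial non-randomized ("The investigators are conducting a non-randomized, open-label, crossover-controlled clinical trial in 50 patients"), while the population table refers to "All randomized patients receiving at least one dose of study treatment"; if all patients used the devices in the same order, treatment and phase would coincide in the model. Second, patients are selected on a positive qualifying test. A reader might infer that the contrast cannot be estimated at all, but the documents do not settle the device sequence, so that conclusion is not available here.

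**What to change.** Reconcile Primary Objectives, Determination of sample size, Statistical Methods and Procedures by one of two routes. Because the trial is open-label, make the choice before anyone sees comparative data, or disclose that it was made later.

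**If non-inferiority is intended:**
- Replace the null with H0: Dosivent minus Aerochamber ≤ −margin.
- Conclude non-inferiority only if the lower limit of the two-sided 95% CI for the treatment difference lies above −margin.
- Have the sponsor define the endpoint and scale of the 3%.
- Give the mL endpoint its own margin, or make it descriptive.
- Restate power for 45 evaluable patients, with the margin, one-sided alpha, assumed true difference, and SD of paired differences with its source.

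**If a test of difference is intended:**
- Remove the 3% limit.
- State the detectable difference, SD with its source, and sidedness.
- Draw no non-inferiority conclusion from a non-significant result.

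**Cost.** Either route is a change of wording with no change to enrolment. The stated power becomes conditional and may look less favourable. For example, at SD 7, margin 3 and one-sided 0.025, it falls from 80.3% to 46.6% if the new device is truly 1 point worse.

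### The mixed model omits each visit's pre-bronchodilator FEV1 or FVC, which is already measured; adding it may narrow the interval, by an amount the plan does not allow one to calculate.

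*Combined protocol and SAP*

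**What the plan says.** - **Endpoints.** The primary objectives are FEV1 change in mL and "changes in forced expiratory volume in the first second (FEV1) in percentage of inhaled salbutamol". The secondary objectives repeat this for FVC.
- **Measurements.** The Schedule of Activities marks the bronchodilator test at Visit 1 and Visit 2, so a pre-dose value exists at each.
- **Model.** Statistical Methods states: "Study variables will be analyzed using linear mixed models representing repeated measures". Patient is random and "treatment and study phase will be the fixed effects". No other covariate is named anywhere, and neither the study variables nor the study phase is defined.
- **Conditions on the test.** Patients are excluded if "Grade A quality spirometry was not obtained according to the classification in current regulation", and Procedures requires a 6-hour salbutamol washout before the repeat test. Nothing limits how far the two pre-dose values may differ.
- **Design.** Methodology describes a "non-randomized, open-label, crossover-controlled clinical trial in 50 patients with a previous positive bronchodilation testing". The modified intention-to-treat population is "All randomized patients receiving at least one dose of study treatment", and the schedule has a randomization step.
- **Decision rule.** Procedures gives a non-inferiority limit of 3%, with no scale stated.

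**The concern.** A change score subtracts the same-day pre-dose value with a slope fixed by definition, and the patient effect absorbs stable differences between patients. Neither removes a remaining dependence of the change on how high or low the patient's pre-dose value was that day. That part stays in the residual. It is most likely to matter for percent change, where the pre-dose value is the denominator.

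At stake is the width of the interval compared with the 3% limit, so the question is mainly one of precision. It touches bias only if the qualifying test with the comparator chamber also supplies the comparator data. Entry requires "increase of Forced Expiratory Volume in first second greater than 200mL and 12" percent on that test, so selection would tend to make the first-visit pre-dose value low and the first-visit change high.

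This assumes that the model is fitted to visit-specific changes. If raw pre- and post-dose values are modelled instead, the pre-dose value is already a response and the point reduces to asking the plan to say so.

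**Working it through.** **1. The plan's own figure.** Determination of sample size gives 45 evaluable patients for 80% power at 0.05 in a paired comparison, with no detectable difference or SD, so 45 cannot be reproduced. Solving backwards (noncentral t, 44 df, two-sided taken as an assumption) gives a standardised paired difference of 0.427. For dropout, 45/0.95 = 47.4, so 48; the stated 50 covers it. I use n = 45; every variance below is an assumption.

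**2. Formula for mL change, balanced order.** Let *a* and *b* be the day-to-day SDs of pre- and post-dose FEV1 and *r* their within-patient correlation. The between-visit difference in change has variance proportional to a² + b² − 2rab. Adjusting for the between-visit difference in pre-dose value leaves b²(1 − r²). With 45 patients, after intercept and sequence, 43 df remain, and estimating the slope costs a factor 1 + 1/(43 − 2) = 1 + 1/41.

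Adjusted/unadjusted variance = b²(1 − r²)/(a² + b² − 2rab) × (1 + 1/41)

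- a/b = 100/100, r = 0.3: 9100/14000 = 0.650; × 1.024 = 0.67
- a/b = 120/100, r = 0.3: 9100/17200 = 0.529; × 1.024 = 0.54
- a/b = 100/120, r = 0.8: 5184/5200 = 0.997; × 1.024 = 1.02

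**3. Simulation, including percent change.** Pre-dose mean was 2000 mL (SD 600, floor 1000).
- Balanced order: sequences of 23 and 22, response 300 mL (SD 100), 80,000 trials per cell.
- Fixed order: response 200 mL (SD 100), entry above 200 mL and 12% on the first test, no phase term, 60,000 trials per cell.

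The balanced mL cells match the formula. Variance ratios, adjusted to unadjusted:

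| Order, scale | a/b | r=0.3 | 0.5 | 0.7 | 0.8 | 0.9 | 0.95 |
|---|---|---|---|---|---|---|---|
| Balanced, mL | 100/100 | 0.67 | 0.77 | 0.87 | 0.92 | 0.97 | 1.00 |
| | 120/100 | 0.54 | 0.62 | 0.69 | 0.71 | 0.70 | 0.63 |
| | 100/120 | 0.78 | 0.89 | 0.99 | 1.02 | 1.00 | 0.90 |
| Balanced, % | 100/100 | 0.61 | 0.67 | 0.75 | 0.76 | 0.77 | 0.73 |
| | 120/100 | 0.50 | 0.55 | 0.58 | 0.57 | 0.52 | 0.45 |
| | 100/120 | 0.71 | 0.80 | 0.90 | 0.95 | 0.99 | 1.01 |
| Fixed, mL | 100/100 | 0.81 | 0.86 | 0.93 | 0.95 | 0.99 | 1.01 |
| | 120/100 | 0.70 | 0.76 | 0.80 | 0.79 | 0.76 | 0.68 |
| | 100/120 | 0.89 | 0.96 | 1.02 | 1.03 | 1.00 | 0.90 |
| Fixed, % | 100/100 | 0.74 | 0.76 | 0.80 | 0.78 | 0.76 | 0.70 |
| | 120/100 | 0.66 | 0.67 | 0.67 | 0.64 | 0.55 | 0.45 |
| | 100/120 | 0.82 | 0.88 | 0.92 | 0.95 | 0.98 | 1.00 |

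**4. Interval width** is the square root of the ratio. For r = 0.3 to 0.8:
- Balanced, mL: √0.54 to √1.02, 27% narrower to 1% wider.
- Balanced, percent: √0.50 to √0.95, 29% to 3% narrower.
- Fixed, mL: √0.70 to √1.03, 16% narrower to 1% wider.
- Fixed, percent: √0.64 to √0.95, 20% to 3% narrower.

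**5. In terms of power.** Let ρ be the correlation between the between-visit differences in pre-dose value and in change. The standardised difference becomes 0.427/√[(1 − ρ²)(1 + 1/42)] on 43 df (paired model without a sequence term). From a starting power of 80%, this gives 79.0% at ρ = 0, 82.7% at 0.3 and 89.2% at 0.5. Break-even is at ρ of about 0.16. With equal SDs ρ² = (1 − r)/2, so break-even is at r = 1 − 2(0.16²), about 0.95, where the table shows 1.00.

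**6. Fixed order with selection on the first test, no true device difference** (r = 0.3 to 0.8). The first-visit pre-dose value is 10 to 67 mL low. The spurious difference (second minus first visit) is −34 to −100 mL unadjusted and −29 to −79 mL adjusted. In percentage points it is −2.1 to −6.2 and −1.4 to −4.2.

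**7. Model checks.** On complete balanced data, a mixed model with both the visit value and the patient mean gives the same device estimate and standard error as the paired regression with a sequence term (−12.72, SE 15.71, in one simulated data set). It also fits with 3 of 50 patients lacking Visit 2 when the mean is taken over available visits. With fixed order, the design matrix has rank 4 of 5: treatment and phase are aliased.

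**The case against.** The strongest reply is that this is an optional refinement. The plan already subtracts the same-day value, removes stable patient differences and restricts spirometry quality. The gain may be nil: some cells reach 1.02 or 1.03. The assumptions also favour a gain. With equal SDs, a negative correlation between pre-dose value and change follows by algebra, −√((1 − r)/2), which is −0.59 at r = 0.3 and −0.32 at r = 0.8. Same-day pre- and post-dose values could plausibly correlate more strongly than 0.8. The undefined response leaves open a reading under which the point disappears. The spurious differences in step 6 measure selection, and under fixed order the covariate moves the estimate as well as its precision.

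All of this is correct, and it lowers the priority of the point. It does not remove it. The documents favour no value of r, so a gain can be neither assumed nor excluded. Higher r does not abolish the gain for percent change at equal SDs (0.77 and 0.73 at r = 0.9 and 0.95, balanced order), although it does at 100/120. The downside in the cells examined is about 3% of variance. The step 6 figures show only that adjustment does not cure selection; they add no weight to this point.

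**Conclusion.** The point holds as a recommendation on efficiency; the unadjusted change-score analysis is valid in this respect. The covariate is absent and the data for it are already collected. The gain ranges from none, or a loss of about 1% in interval width, to an interval more than a quarter narrower. Where the trial falls depends on SDs and a correlation that the plan does not give. The conclusion rests on the visit-specific change being the response.

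It ranks below two design questions: whether device order is randomized, on which the documents contradict themselves, and whether the qualifying test is also the comparator measurement. If order is fixed, no covariate separates device from phase. If entry is selected on the comparator test, adjustment only partly reduces the bias.

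**What to change.** Before the data are analysed:

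1. State that the response is the visit-specific change. If raw pre- and post-dose values are modelled instead, say so; the covariates below are then unnecessary.
2. Add the visit's pre-dose FEV1 (FVC for the secondary endpoints) and the patient's mean pre-dose value over available visits. The second term keeps the within-patient slope apart from differences between patients, and a patient who misses Visit 2 still has a defined value.
3. Define study phase. Keep that term where device order varies between patients. If order is fixed, state that treatment and phase cannot be separated and that the covariate does not change this.
4. Report the unadjusted model as a sensitivity analysis.

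The cost is one or two sentences, no new measurements, and one or two degrees of freedom. If there is no residual dependence, that is about 2% of variance (1/41), or about one point of power from 80%; the worst simulated cell lost 3% of variance.
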